6.2. Screening

At the screening visit, each potential subject will be allocated a Subject Identification Number for tracking purposes and it is intended to assure confidentiality for subjects.

A full medical history including concomitant medications and physical examination will be performed in accordance with standard of care. Subjects will be assessed according to the eligibility criteria. They will not undergo any tests or procedures that are study specific and are not standard clinical practice.

The screening visit may be combined with the baseline visit.

Subjects who do not meet the eligibility criteria are regarded as screen failures. A screening log should be kept and will be a record on all subjects screened identified by the Subject Identification number. For screened failures, the eligibility criterion/ criteria that are not met should be recorded.

6.3. Enrolment

Only subjects who meet the eligibility criteria will be approached to participate in the study. Subjects are enrolled into the study after providing signed informed consent to participate in the study.

6.4. Informed Consent Process

The Informed Consent Form can only be used after the clinical investigation has been fully approved by the Competent Authority and Institution's Ethics Committee (EC). The Sponsor or their CRO representative should be informed on the approved Informed Consent form before it is implemented in the study.

When the Investigator has determined the eligibility of a specific subject to enter this study, the Investigator will provide an informed consent form to the subject. The Investigator or designee will discuss and explain the clinical investigation with the subject as following:

- include a description of all aspects of the clinical study that are relevant to the subject's decision to participate throughout the clinical study,
- avoid any coercion of or undue influence of subjects to participate,
- not waive or appear to waive subject's legal rights,
- use native language that is non-technical and understandable to the subject or his/her legal representative,
- provide ample time for the subject to consider participation and ask questions if necessary,
- ensure important new information is provided to new and existing subjects throughout the clinical study.

The Investigator will obtain a signed informed consent form from the subject before performing the TIES® implant procedure or any protocol-specific tests. The Investigator will provide subjects with a copy of their signed informed consent form. The Investigator will provide new information to new and existing subjects.

The Investigator will maintain a copy of the EC-approved Informed Consent Form along with a copy of each subject's signed Informed Consent Form in a designated study file.

CLINICAL INVESTIGATION PLAN

6.5. Baseline Visit

The baseline visit may be combined with the screening visit. A full medical history including concomitant medications and physical examination will be performed in accordance with standard of care. Subjects will be assessed according to the eligibility criteria. They will not undergo any tests or procedures that are study specific and are not standard clinical practice until informed consent has been provided.

Each subject will be given a Subject Identification Number for tracking purposes and it is intended to assure confidentiality for subjects.

After confirming that all the inclusion and exclusion criteria are met, Informed consent will be discussed.

The following examinations are regarded as part of pre-operative assessment and the results are to be recorded in the medical case notes in accordance with requirements of the institution where the surgical procedure will be performed:

- Demographics, medical history and concomitant medications
- Physical examination
- Pregnancy test in woman of childbearing potential
- Pre-operative ECG
- Hematology and Chemistry
- Dipstick urine analysis
- Assessment by the stoma/research nurse and siting of stoma if required

The following information will be collected in the case report forms (CRFs):

- Demographics
- Medical history including indications for ileostomy and previous surgeries
- Concomitant medications
- Document in CRFs if the following procedures have been performed and any abnormal findings: physical examination, pre-operative ECG, hematology and chemistry tests, dipstick urine analysis
- Record if pregnancy test has been performed and the result
- Record if assessment by the stoma/research nurse has been performed and any abnormal findings
- Quality of Life (QoL) Questionnaire/s

6.6. TIES® Port Implantation Procedure

Detailed instructions on implanting the TIES® Port and on connecting the distal ileum to the TIES® Port can be found in the Surgical Procedure Manual (see Appendix).

6.6.1. Subject Preparation

The subject will be prepared for the implantation surgery, per the Surgical Procedure Manual (see Appendix), and per the hospital's standard for ileostomy surgeries including siting of the stoma prior to surgery.

6.6.2. Implantation Procedure

Performance on the implantation procedure will be captured as well as any Adverse Events (AE) that occurred during the procedure. A list of the TIES® surgical aids used should be recorded. Any changes in the doses or discontinuation of concomitant medications will also be documented.

CLINICAL INVESTIGATION PLAN

6.6.3. Post operation care

The patient will be followed up daily before their discharge for the stoma/device and general health condition, as follows:

- Adverse Event and safety evaluation
- Changes in concomitant medications
- Cleaning procedure according to patient's needs (the same as used in conventional ileostomies) will be performed; the stabilizer can be left in place during cleaning.

6.6.4. Bail Out Procedure (if applicable)

All bailout procedures, that is, conversion to a conventional ileostomy, and all adverse events associated with the procedure should be documented.

Refer, also, to section 6.16.2 on explant procedure.

6.7. Hospital Discharge

Before discharge from the hospital, the following study assessments/activities will be performed:

- Examination of the subject and the stoma
- Photographs of the stoma and adjacent skin
- Adverse Event evaluation
- Record any changes in concomitant medications
- Cleaning procedure, according to schedule will be performed;
- Instructions provided to the patients on care of the stoma.

○ A patient's guide on care of the implant and use of the TIES® Lid for the first 16 weeks after implantation is included in the Appendix.

6.8. Turnbull Adaptor Removal

The Turnbull Adaptor will be removed at 4 weeks (+/- 7 days) if it has not already detached from the stoma. The patient will continue to use a stoma bag for several weeks after that time until the stoma is sufficiently healed to allow introduction of the TIES® Lid and subsequent regular use of the TIES® Lid.

6.9. Follow-Up Visits

Follow-up visits for this study are planned at 4, 8, 16, 24, 36 and 52 weeks after the implantation procedure. They are named consecutively from Visit 1 to Visit 6. All visits are office visits except for Visit 5 at 36 weeks and Visit 6 at 52 weeks that can be conducted via video-conferencing if the subject is unable/unwilling to make the journey. The subject will be instructed to take photographs and forward these to the site. An office visit might still be carried out depending on the assessment during the video-conference.

Unscheduled office visits can be carried out if there is a medical need.

For subjects who require a second implant, the timing of the follow-up visits will commence after the new implantation procedure.

For subjects who require a revision of the implant, the timing of the follow-up visits may or may not need to be readjusted following the revision procedure, based on the assessment by the investigator.

Photographs showing the implant and peristomal skin will be taken to as study documentation at every follow-up visit as described below in section 6.12.

CLINICAL INVESTIGATION PLAN

The following assessments/activities will be performed at follow-up visits.

6.9.1. Visit 1 at 4 weeks (+/- 7 days) at the office

- Physical examination including evaluation of ingrowth into the stoma
- Inspect healing around the stoma and implant
- Review and instruct on care of the stoma
- Removal of Turnbull Adaptor if it has not already detached from the stoma (see Surgical Procedure Manual, in Appendix)
- Adverse event and safety evaluation
- Concomitant medications review
- Photographs of the implant, stoma and adjacent skin

6.9.2. Visit 2 at 8 weeks (+/- 7 days) at the office

- Physical examination including evaluation of ingrowth into the stoma
- Evaluate if the healing around the implant is sufficient for start of TIES® Lid use
 - Trimming of excess intestinal tissue to about 5 mm above the top of the cylinder of the Port if required
 - If trimming is performed, postpone start of use of TIES® Lid by one week for healing
- Review and instruct on care of the stoma
- Adverse event and safety evaluation
- Concomitant medications review
- Photographs of the implant, stoma and adjacent skin
- Complete EQ-5d and Montreux Quality of Life Questionnaires
- Provide instructions on the 72-hour subject's diary to be completed prior to the next visit

6.9.3. Visit 3 at 16 weeks (+/- 7 days) at the office

- Physical examination including evaluation of ingrowth into the stoma
- Review and instruct on care of the stoma
- Adverse event and safety evaluation
- Concomitant medications review
- Photographs of the implant, stoma and adjacent skin
- Review if the required 72-hour subject's diary has been completed and provide the subject a new diary to complete prior to the next visit
- Review if the required EQ-5d and Montreux Quality of Life Questionnaires have been completed

6.9.4. Visit 4 at 24 weeks (+/- 14 days) at the office

- Physical examination including evaluation of ingrowth into the stoma

CLINICAL INVESTIGATION PLAN

- Review and instruct on care of the stoma
- Adverse event and safety evaluation
- Concomitant medications review
- Photographs of the implant, stoma and adjacent skin
- Review if the required 72-hour subject's diary has been completed and provide the subject a new diary to complete prior to the next visit
- Review if the required EQ-5d and Montreux Quality of Life Questionnaires have been completed

6.9.5. Visit 5 at 36 weeks (+/- 14 days) at the office or via video-conferencing

- Physical examination including evaluation of ingrowth into the stoma
- Review and instruct on care of the stoma
- Adverse event and safety evaluation
- Concomitant medications review
- Photographs of the implant, stoma and adjacent skin
- Review if the required 72-hour subject's diary has been completed and provide the subject a new diary to complete prior to the next visit
- Review if the required EQ-5d and Montreux Quality of Life Questionnaires have been completed

6.9.6. Visit 6 at 52 weeks (+/- 14 days) at the office or via video-conferencing

- Physical examination including evaluation of ingrowth into the stoma
- Review and instruct on care of the stoma
- Adverse event and safety evaluation
- Concomitant medications review
- Photographs of the implant, stoma and adjacent skin
- Review if the required 72-hour subject's diary has been completed and provide the subject a new diary to complete prior to the next visit
- Review if the required EQ-5d and Montreux Quality of Life Questionnaires have been completed
- Complete subject's preference questionnaire

6.10. Unscheduled Visits

Subject may contact the investigator or the stoma/research nurse at any time outside of the scheduled follow-up visits. If there is a need for an unscheduled visit, for example, to evaluate adverse events, this should be documented in the case report forms.

6.11. Follow-up treatment after end of investigation

The investigation sponsor will provide explantation of the device during the clinical investigation if necessary (see Explantation procedure, below). At the end of the investigation, subjects have the right to choose whether to retain the device or to have the device removed. The same applies should the investigation be temporarily halted, or early terminated. The decision will be made in accordance with the investigator and based on

CLINICAL INVESTIGATION PLAN

investigator judgement. If the subject keeps the device in place, the subject will be followed up by his/her general stoma team per standard stoma care and standard care for a non CE-marked device outside the investigation.

6.12. Photography of the stoma including the implant and peristomal skin

Photographs should be taken to show extent of ingrowth into the implant and around the implant at every visit and as needed if any complications develop. The photographs should include the peristomal skin, particularly if peristomal skin lesions are noted or suspected. The subject identification number, the view and the Visit number are to be included in the photographs.

The following views are required:

1. Horizontal view with the subject in the supine position:
 - "Horizontal View (HV)" – photograph of the implant and peristomal skin from above;
2. 3 Vertical views with the subject standing upright:
 - Vertical frontal view (FV) – photograph of the implant and peristomal skin taken from the front,
 - Vertical right view (RV) – photograph of the implant taken from the right, and,
 - Vertical left view (LV) – photograph of the implant taken from the left.

The photographs are to be uploaded into the electronic case report form system. Care should be taken so that the identity of the subject is not disclosed in the photographs. The files should be labelled by renaming the image file using the following convention study comprising of number_subject ID_photograph view_visit number, eg TIESIIIC03_9901_RV_4 weeks.

A printed copy of the photographs should be kept as part of medical records at the site and these should be labelled by the subject number, the view and the Visit number.

6.13. Quality of Life (QoL) Questionnaires

Quality of Life questionnaires will be provided to the subjects, with instructions on how and when the questionnaires should be completed at baseline and from Visit 2 onwards. The QoL questionnaires can be completed either prior to the visit or during the office visit. These questionnaires can be filled in on the internet or on paper. Those QoL questionnaires include:

- EQ-5d quality of Life Questionnaire
- Montreux Quality of Life Questionnaire (specific to stomas)

See Appendix for more details on the QoL questionnaires.

6.14. TIES® System Performance Evaluation Questionnaire – Subject's diary

A TIES® System Performance Evaluation Questionnaire will be provided to the subjects in the form of a 72-hour diary, with instructions on how and when the questionnaire should be completed per the study visit schedule. See Appendix for more details.

6.15. Subject's Preference Evaluation

A Subject's preference questionnaire will be provided to the subjects to respond to at the last study visit at 52 weeks. Appendix for more details.

CLINICAL INVESTIGATION PLAN

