4.1. Performance Evaluation

Performance evaluation is based on subject's assessment of performance as recorded on the 3-day diary preceding each scheduled follow-up at 16, 24, 36 and 52 weeks after operation. Performance evaluation applies only among subjects with the TIES® Port *in situ*.

Among subjects with the TIES® Port *in situ*, performance will be assessed according to (a) the proportion of subjects who use the TIES® Lid for continence control; (b) the proportion of subjects experiencing visible leakages around the implant; and (c) subject's assessment on the ease of use of the TIES® Solution.

Primary endpoint is absence of visible leakage or fecal staining of clothing at 24 weeks after implantation of the TIES® Port.

The success criterion at 24 weeks requires at least 70% of subjects with the TIES® Port *in situ* having no visible leakage or staining of clothing adjacent to the implant between consecutive episodes of using the lid for continence control. Spillage that might occur at opening of the lid is not regarded as leakage.

Secondary endpoints are

CLINICAL INVESTIGATION PLAN

- Absence of visible leakage or fecal staining of clothing at 16, 36 and 52 weeks.
- Proportion of implanted subjects using the TIES® Lid for continence control at 16, 24, 36 and 52 weeks.
- Subject's assessment on the ease of use of the TIES® Lid using a visual analog scale 16, 24, 36 and 52 weeks after implantation.
- Subject's preference for the TIES® solution assessed at 52 weeks.

The subject's assessment on the ease of use of the TIES® Lid will provide feedback to the manufacturer regarding future refinements of the TIES® solution. Information will be collected in the diary to understand patient's needs as described in section 10.

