5.3.4. Withdrawal

Early termination of study participation will be documented for patients that have signed an informed consent form and who exited for any of the following reasons:

- Subject for whom the implantation procedure has been attempted but cannot completed, for example, due to technical reasons. (These subjects will be followed for six months.)
- Subject who are explanted. (These subjects will be followed for six months.)
- Subject no longer wishes to continue with the study follow-up. No further follow up applies.
- Investigator believes it is the best medical interest of the subject to discontinue study participation due to safety reasons. (These subjects will be followed until study procedure related adverse events have resolved.)
- Death of the subject.

No additional subjects will be recruited to compensate for subjects who withdraw or are withdrawn from the study.

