6.17.2. Withdrawal

Subjects may withdraw from the study at any time, with or without reason and without prejudice to further treatment. Withdrawn subjects will not undergo any additional study follow-up. The reason for withdrawal will be recorded (if given) in all cases of withdrawal. The investigator may discontinue a subject from participation in the study if the investigator feels that the subject can no longer fully comply with the requirements of the study or if any of the study procedures are deemed potentially harmful to the subject. No new data will be collected after withdrawal from the study. Data that have already been collected on withdrawn subjects will be retained and used for analysis, unless disallowed by national or local regulations.

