10.3. Study Population Definition

The study population is defined according to the Intent-to-Treat principle. All enrolled subjects will be taken into consideration in the reported results, without any planned exclusion.

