10.10.3. Subject's preference

Because the subjects will need to use stoma bags continuously for at least the first 8 weeks and then intermittently until the TIES® Lid can be used regularly, it is of interest to obtain their assessment on how the two alternatives may influence their wellbeing. Four topics from the 2 quality of life questionnaires have been selected for comparisons. This assessment will be performed at the last study visit at 52 weeks. The subjects will be asked the following questions about their experience with the use of the TIES® Solution compared to the continuous use of stoma bags.

1. Regarding maintaining body hygiene
 - a) No difference with using either stoma bags that collected waste continuously or TIES® Lid for periodic emptying of waste
 - b) Easier with stoma bags that collected waste continuously
 - c) Easier with TIES® Lid for periodic emptying of waste
2. Regarding daily activities (e.g. work, study, housework, family or leisure activities)
 - a) No difference with using either stoma bags that collected waste continuously or TIES® Lid for periodic emptying of waste
 - b) Easier with stoma bags that collected waste continuously
 - c) Easier with TIES® Lid for periodic emptying of waste
3. How worried were you about odor from your stoma?
 - a) No difference with either stoma bags that collected waste continuously or TIES® Lid
 - b) Less worry with stoma bags that collected waste continuously
 - c) Less worry with TIES® Lid for periodic emptying of waste
4. How worried were you about leakage from your stoma?
 - a) No difference with either stoma bags that collected waste continuously or TIES® Lid for periodic emptying of waste
 - b) Less worry with stoma bags that collected waste continuously
 - c) Less worry with TIES® Lid for periodic emptying of waste
5. Would you recommend the TIES® solution to friends or family members who need to undergo ileostomy?
 - a) No
 - b) Undecided
 - c) Yes

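### Preference is asked only at week 52, so the result is an unlabelled survivor estimate that omits early explants who were not re-implanted

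*Combined protocol and SAP*

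**What the plan says.** The document places the preference measure at one time point throughout.

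- Section 4.1 lists among the secondary performance endpoints: "Subject's preference for the TIES® solution assessed at 52 weeks".
- Section 6.15 says that the preference "questionnaire will be provided to the subjects to respond to at the last study visit at 52 weeks". Section 10.10.3 repeats it: "This assessment will be performed at the last study visit at 52 weeks". The visit list ("Complete subject's preference questionnaire", under Visit 6 in section 6.9.6) and the schedule of assessments agree.
- The population rule in sections 4.1 and 10.4 is: "Performance evaluation applies only among subjects with the TIES® Port" in situ.
- Section 5.3.4 counts explantation as early termination: "Subject who are explanted. (These subjects will be followed for six months". It does not say when the six months start.
- Section 6.17.2 says of withdrawals: "Withdrawn subjects will not undergo any additional study follow-up". It also bars new data after that point.
- Section 6.9 restarts the visit clock for a subject who receives a second implant.
- Section 10.9 plans no replacement of missing data, bases percentages on non-missing observations, and also reports the number missing.
- Section 10.3 nevertheless states: "All enrolled subjects will be taken into consideration in the reported results, without any planned exclusion".

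**The concern.** The questionnaire asks subjects to compare the Lid with continuous bag use on four topics, and whether they would recommend the device. Section 3.1 relies on it: with no control arm, each subject's own experience of both methods is offered as the comparison with the stoma bag. Subjects who tried the Lid and then had the Port removed hold an important part of that comparison, and the schedule does not reach those removed early.

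At stake is how a favourable percentage will be read. Without a label it looks like the view of the implanted population, whereas it is the view of those who kept the Port for a year. Answers that were not collected cannot be recovered at analysis.

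**Working it through.** **1. The plan's own figures.** The plan gives no rate, target or precision for preference. Its only design calculation is the power table in section 10.5 for the primary leakage endpoint. That table reproduces with power = Φ((p − 0.60)/√(p(1 − p)/n) − 1.96). For p = 0.70 and n = 200: √(0.21/200) = 0.0324, 0.10/0.0324 − 1.96 = 1.13, and Φ = 87.0%. For n = 180, 160, 140 and 120 it gives 83.3, 78.8, 73.3 and 66.7%, against 83, 79, 73 and 67% in the table. All 30 cells agree within 0.5 point. The table is not in dispute and is not touched by this point.

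**2. Who is asked.** Six months is about 26 weeks, and Visit 6 has a window of ±14 days.

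| Situation | Asked at week 52? |
|---|---|
| Explanted, not re-implanted, six months counted from explantation | No if removed before 52 − 26 = week 26 (before week 24 if the visit falls at week 50) |
| Explanted before week 26, not re-implanted, six months counted from implantation | No; leaves at about week 26 |
| Explanted later, six months counted from explantation | Possibly still in follow-up, but outside the in-situ population |
| Second implant | Can be asked; the clock restarts |
| Withdrawn before week 52 | No |
| Port in situ at week 52, satisfied or not | Yes |

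Subjects explanted before Lid use starts, at about week 8, cannot compare Lid with bag. The group that matters is therefore subjects who used the Lid and then lost the Port.

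**3. Size.** Let e be the share of Lid users not asked, P_resp the share favourable among those asked, and P_expl the share favourable among those not asked. Then

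P_all = (1 − e)·P_resp + e·P_expl, and overstatement = P_resp − P_all = e·(P_resp − P_expl).

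The documents give none of these three values. Assuming P_resp = 70% and P_expl between 0 and 40%:

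| e | P_all | Overstatement (points) |
|---|---|---|
| 5% | 66.5 to 68.5% | 1.5 to 3.5 |
| 10% | 63 to 67% | 3 to 7 |
| 20% | 56 to 64% | 6 to 14 |
| 30% | 49 to 61% | 9 to 21 |

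With P_resp = 80%, the range at e = 20% is 8 to 16 points. If P_expl = P_resp the overstatement is zero.

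**4. Bounds without assuming P_expl.** Suppose all 200 subjects are implanted and try the Lid, 40 are not asked, and 112 of 160 (70%) are favourable. The figure for all 200 lies between 112/200 = 56% and (112 + 40)/200 = 76%.

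**5. Against sampling error.** The 95% half-width at n = 160 is 1.96 × √(0.21/160) = 7.1 points. At e = 20% the selection effect is of similar size or larger under these assumptions, and the planned confidence interval does not reflect it.

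**6. Plausible range of e.** Section 10.5 works with 80% evaluable at 24 weeks; nothing is given for week 52. In the two earlier studies (section 1.5), 10 of 11 Ports stayed beyond 6 months and 5 of 11 beyond 12 months, so 1/11 (9%) and 6/11 (55%) did not. Section 1.3 says that eligibility has since been refined, so these shares are a caution and not a forecast.

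**The case against.** The strongest reply is that preference is a performance endpoint, and performance is declared only for subjects with the Port in situ. Explanted subjects are then outside the endpoint by definition, and the 52-week figure correctly answers a question about continuing users. Wanting an all-user figure is wanting a different estimand. Attrition will also be visible elsewhere: the number missing is reported, Port removal has its own lifetable analysis, safety covers all implanted subjects, and Lid and bag use is recorded in diaries from week 16.

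Much of this stands. The figure is a valid survivor estimate and needs a label more than a correction. But because explanted subjects fall outside the in-situ population, the count of missing answers need not include them, and neither the lifetable nor the diaries say whether a former Lid user preferred the Lid or the bag.

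A reader might also infer three stronger claims that the documents do not support:

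- **That everyone whose Port is removed early is never asked.** Second implants restart the clock, and later explants may still be in follow-up at week 52.
- **That the direction of bias is established.** No data on the preferences of early leavers are given. Section 4.2 foresees removals unrelated to device performance, section 1.5 reports explantation as part of hernia repair, and section 6.17.3 withdraws subjects for pregnancy. Dissatisfied subjects who keep the Port are still asked.
- **That the questionnaire's timing creates the conflict with section 10.3.** The tension between that statement and the in-situ restriction runs through all performance and quality-of-life endpoints.

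**Conclusion.** The point holds as a cheap improvement to a descriptive secondary endpoint. Subjects explanted before about week 24 to 26 and not re-implanted are not asked, later explants may be excluded from the analysis, and the resulting percentage applies to subjects with the Port in situ at 52 weeks.

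It probably overstates preference among all implanted subjects who tried the Lid, because removal is likely to go with dissatisfaction. That is a judgement and not a documented fact. The 6 to 14 points at 20% not asked rest on assumed rates of 70% among respondents and 0 to 40% among the rest; the true size is unknown and could be zero.

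The documents do not support calling the endpoint invalid. Nor do they support extending the point to the primary endpoint or its power: section 10.9 plans no test of preference, and no success criterion depends on it.

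**What to change.** - **Collection (sections 6.15 and 10.10.3 and the schedule of assessments).** Keep the week-52 administration. Also give the five-question form to explanted subjects who have used the Lid, at explantation or during their existing six-month follow-up.
- **Withdrawals.** The plan has no withdrawal visit, and section 6.17.2 bars new data afterwards. Offer the form on a voluntary basis at the contact where the subject announces withdrawal, before it takes effect.
- **Reporting (section 10.10.3 and the statistical analysis plan still to be written).** Label the 52-week result as Port in situ at 52 weeks. Beside it, report the result for all implanted subjects who ever used the Lid, with the number not asked. Add a sensitivity analysis that counts explanted or missing subjects as not preferring the device.

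The cost is a minor CRF and schedule change. Coverage of voluntary withdrawals will be incomplete, the all-Lid-user figure will mix answers given at different times after implantation, and it may be less favourable than the in-situ figure. The change helps only subjects who have not yet left the study, so it should be made early.
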